7.1 Study Design

Describe and explain the study design.

A two-arm randomized parallel study is proposed. Subjects will be randomized to one of the following attention and resource matched conditions for approximately 12-weeks: 1) education to consume 2 oz./day of pecans in place of the snacks they usually eat (AAD+P); 2) continue consuming their current diet (AAD) with provision gift cards worth \$30 monthly (equivalent value to the pecans) and matched contact with study personnel.

Assessment of outcomes will occur at baseline and the end of the treatment period (week 12). Pre-menopausal women will be scheduled for testing within 7 days of starting their menstrual period to control for hormonal effects on vascular function. Therefore, the treatment periods may be adjusted as needed. At the baseline and 12-weeks two blood samples will be collected (separated by at least 24-hours) for endpoint analysis. Weight will be measured on both days at each timepoint. Flow mediated dilation, central and peripheral blood pressure and pulse wave velocity will be measured on one day at each time point. Diet intake will be assessed at baseline, week 6, and week 12 using 24-hour recalls. Subjects will also provide a fecal collection at baseline and 12 weeks.

7.2

Study Procedures

Provide a step by step description of all research procedures being conducted (broken down by visit, if applicable) including such information as below (where and when applicable); describe the following:

- HOW: (e.g., data collection via interviews, focus groups, forms such as surveys and questionnaires, medical/school records, audio/video/digital recordings, photographs, EKG procedures, MRI, mobile devices such as electronic tablets/cell phones, observations, collection of specimens, experimental drug/device testing, manipulation of behavior/use of deception, computer games, etc.)
- WHERE: (e.g., classrooms, labs, internet/online, places of business, medical settings, public spaces, etc.)

[Type protocol text here]

7.2.1 Visit 1 or Day 1 or Pre-test, etc.

Provide a description of what procedures will be performed on visit 1 or day 1 or pre-test in order of how these will be done. If your study only involves one session or visit, use this section only and indicate 7.2.2 as not applicable.

Participants will be consented prior to any screening activities.

Screening: This visit will occur at the Clinical Research Center, Noll Laboratory. The clinical visit will consist of filling out forms (medical history, personal information); measuring waist circumference and height and weight so that BMI can be calculated and blood pressure will be measured to determine eligibility. Women of child-bearing potential will provide a urine sample for a pregnancy test. A blood sample will be taken and a complete blood count, and a blood lipid panel will be performed (approximately 19 ml of blood or ~1.25 tablespoon will be taken). If the initial blood draw is unsuccessful it may need to be repeated, with permission from the participant. In addition, if a potential participant takes thyroid medicine they must provide a current (within 6 months) lab test. If they do not have one, an extra 3.5 ml (0.2 Tbsp) of blood will be taken to conduct a thyroid test. If all eligibility criteria are met, participants will be scheduled for their baseline measurements. Baseline visits typically occur within 1-2 weeks following the screening appointment. Participants will be provided with one of two standardized meals with foods commonly consumed in the American diet prepared in the metabolic diet center kitchen to consume the evening before their Day 2 visit. The meal options will be Mediterranean chicken with potatoes and broccoli OR a black bean quesadilla with broccoli.

7.2.2 Visit 2 or Day 2 or Post-test, etc. (If applicable)

Provide a description of what procedures will be performed on visit 2 or day 2 or post-test in order of how these will be done. If your study involves more than two sessions or visits replicate this section for each additional session or visit (e.g., 7.2.3, 7.2.4, etc.).

*Vascular testing may occur on day 1 or day 2 based on participant's availability

Baseline and Endpoint Measurements (Day 1)

Measures will be collected at baseline and 12 weeks. At each timepoint, fasting blood samples will be collected for analysis of biochemical endpoints. Body weight will be taken, and vascular health assessments will be performed at baseline and week 12. Participants will also complete a fecal collection at the beginning and end of the treatment period. Participants will complete three, 24-hour dietary recalls at baseline, week 6 and week 12 for a total of 9 dietary recalls. Participants will be provided a standardized meal for dinner.

Central and peripheral blood pressure: Following a 5-minute rest period, brachial artery systolic and diastolic blood pressure will be measured in the left arm using an automated blood pressure cuff. The cuff will reinflate and obtain a pulse wave form. Central blood pressure and wave reflection characteristics (augmentation index) will then be derived from the pressure waveforms using a validated transfer function with a SphygmoCor System (AtCor Medical, Sydney, Australia). This test will be performed in triplicate.

Pulse Wave Velocity: Arterial stiffness will be assessed by calculating the pulse wave velocity (PWV) between the carotid and femoral arteries while in the supine position. A cuff will be placed on the participant's thigh. The cuff will inflate during the test to record the pulse waveform in the femoral artery. A simultaneous measurement of the carotid artery pressure waveform will be obtained by an applanation tonometry sensor manually held in place above the carotid artery. PWV will subsequently be calculated by dividing the linear distance between the carotid and femoral sites by the transit time using the SphygmoCor system (AtCor Medical, Sydney Australia). This measurement will be performed in triplicate.

Plasma/serum analysis: In addition to the blood taken at screening, 12 hour fasting blood samples also will be taken. Approximately 45 ml (about 3 Tbsp) will be collected at each visit. A typical American Red Cross blood donation is 1 pint (500 ml). Blood may be analyzed for the following: blood lipids and lipoprotein concentration, particle number and size, glucose and insulin, other markers of glycemia, cholesterol metabolism, and/or inflammation.

Fecal collection: At baseline and the end of each treatment period, participants will be asked to collect a stool sample (~50 g). They will be provided with a stool sample kit and detailed instructions for collection of a clean sample on Day 1 of testing and asked to bring in the collected sample on Day 2; if an individual is not able collect the sample within this timeframe alternative arrangements will be made to accommodate the subject. Fecal samples will be analyzed for gut bacteria composition (gut microbiome).

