7.2.3 Day 2 of Baseline and Endpoint Measures

On day 2 of baseline and endpoint visits, which occur approximately 24 hours after day 1 testing, a fasting blood sample will be collected and flow mediated dilation measures will be taken. Body weight will be taken. Fecal sample collection will be brought to the visit by the subject.

Flow mediated dilation: Study subjects will undergo endothelial health assessment by FMD at baseline (beginning of study) and end of each intervention period. The technique of FMD is a non-invasive test that assesses endothelium-dependent dilatation in response to increased blood flow. Blood flow is induced by inflation and deflation of a cuff on the forearm. The cuff should be inflated to suprasystolic pressures in order to occlude the brachial artery. A pressure of 250 mmHg is a standard pressure used by many research groups. B-mode ultrasound is used to assess endothelium-dependent vasodilation.

Plasma/serum analysis: A 12 hour fasting blood sample will be taken. Approximately 45 ml (about 3 Tbsp) will be collected at each visit. A typical American Red Cross blood donation is 1 pint (500 ml). Blood may be analyzed for the following: blood lipids and lipoprotein concentration, particle number and size, glucose and insulin, other markers of glycemia, cholesterol metabolism, and/or inflammation.

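### Does letting vascular testing fall on Day 1 or Day 2, with no matching of test day or dinner between baseline and week 12, weaken the FMD result?

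*Protocol*

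**What the plan says.** Protocol Section 7.1 sets one FMD measurement day per time point: "Flow mediated dilation, central and peripheral blood pressure and pulse wave velocity will be measured on one day at each time point". The sentence before it says of weight: "Weight will be measured on both days at each timepoint". Section 7.2.3, headed as Day 2, assigns FMD to that day: "a fasting blood sample will be collected and flow mediated dilation measures will be taken". A note at the top of Section 7.2.2 reads "Vascular testing may occur on day 1 or day 2 based on" the participant's availability. It does not name FMD. The time estimates in Section 7.3 list vascular testing on both days.

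The screening paragraph in Section 7.2.1 describes a standardised dinner "to consume the evening before their Day 2 visit", with two choices: "The meal options will be Mediterranean chicken with potatoes and broccoli OR a black bean quesadilla with broccoli". Section 7.2.2, under Day 1 of the baseline and endpoint visits, adds "Participants will be provided a standardized meal for dinner". No sentence provides such a dinner before Day 1, and none requires the same day or dinner at both time points.

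Other controls are stated. Blood draws on both days follow a 12-hour fast (Sections 7.2.2 and 7.2.3), and for hormonal effects: "Pre-menopausal women will be scheduled for testing within 7 days of starting their menstrual period to control for hormonal effects on vascular function". The SAP compares change from baseline, adjusted for baseline value, age, sex and BMI. It averages weight, lipids, glucose and insulin over the two test days; FMD is not in that list.

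**The concern.** FMD carries the sample size and the main conclusion. It is taken on one day per time point, so day-to-day variation is not averaged out, and the model has no term for test day or meal. If the Section 7.2.2 note includes FMD, a participant could be tested on Day 2 after a standardised dinner at baseline and on Day 1 after an uncontrolled dinner at week 12, or the reverse. Even with Day 2 both times, the two dinners could differ. Either mismatch would enter the change score as extra variance. Planned power has almost no slack above 80%, and the trial already supplies a standardised dinner, so extending it to every FMD test looks like a cheap improvement.

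**Working it through.** **Inputs.** Difference 1.2 points, SD 2.4, 80% power, alpha 0.05, 64 per group (Protocol Sections 8.1 and 8.2; SAP). The SAP puts the 1.2 on the change scale, so 2.4 is read as the SD of the change. Sidedness is not stated; two-sided is assumed. The documents give neither the share of participants mismatched (f) nor the SD that a mismatch adds to the change (s), so both are assumptions shown over a range.

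**1. The plan's figure.** For a two-sample t test with 64 per group, the noncentrality is 1.2 / (2.4 × √(2/64)) = 2.828 on 126 degrees of freedom. Power is 80.146%, that is 80.1%. At 63 per group it is 79.5%, so 64 is the smallest number that reaches 80%. The stated 128 reproduces.

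**2. Reading the passages together.** Sections 7.2.1 and 7.2.2 fit one schedule: Day 1 visit, standardised dinner that evening, Day 2 visit with FMD. Followed at both time points, every FMD test comes after a standardised dinner and only the choice of dinner can differ. The larger gap, a Day 1 FMD test with no standardised dinner before it, needs the Section 7.2.2 note to cover FMD. Section 7.1 groups FMD with the other vascular measures, which favours that reading. Against it, the note heads a section describing blood pressure and pulse wave velocity, and Section 7.2.3 gives FMD its own day with no alternative.

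**3. Is there a mechanism?** The only timed acute effect of a food on FMD in the documents is in Section 2.1: cocoa flavanols, lasting 2 to 3 hours. The visits include a 12-hour fasting draw, at least 12 / 3 = 4 times as long. This is indirect, since cocoa is not dinner, but it points towards a small or zero effect. Nothing in the documents points the other way.

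**4. Size on assumed inputs.** Two cases, with 2.4² = 5.76:

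- Noise comes on top of SD 2.4: SD = √(5.76 + f·s²); participants lost in effect per group = 64 × (1 − 5.76/SD²).
- Noise is already inside SD 2.4 and matching removes it: SD = √(5.76 − f·s²); lost week-12 tests per group that would cancel the gain = 64 × f·s²/5.76.

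| f | s | f·s² | Power, noise on top | Lost in effect per group | Power after matching, noise inside | Break-even lost tests per group |
|---|---|---|---|---|---|---|
| any | 0 | 0 | 80.15% | 0 | 80.15% | 0 |
| 0.25 | 0.25 | 0.0156 | 80.04% | 0.17 | 80.25% | 0.17 |
| 0.50 | 0.25 | 0.0313 | 79.93% | 0.35 | 80.36% | 0.35 |
| 0.25 | 0.5 | 0.0625 | 79.72% | 0.69 | 80.57% | 0.69 |
| 0.50 | 0.5 | 0.125 | 79.30% | 1.36 | 81.00% | 1.39 |
| 0.25 | 1.0 | 0.25 | 78.46% | 2.66 | 81.85% | 2.78 |
| 0.50 | 1.0 | 0.50 | 76.80% | 5.11 | 83.58% | 5.56 |

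Example, last row: √(5.76 + 0.50) = 2.502, and 64 × (1 − 5.76/6.26) = 5.11.

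**5. Offset from the model.** If 2.4 is an unadjusted SD, the planned covariates restore 80.1% power, ignoring the few degrees of freedom they use, once they explain 1 − 5.76/SD² of the variance. That is 1.1% (f 0.25, s 0.5) to 8.0% (f 0.50, s 1.0).

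**6. Bias.** An arm difference would need week-12 test day to differ by arm. The bias would be the difference in Day 1 shares times the day shift; for example, 0.2 × 0.5 = 0.1 points against a target of 1.2. Nothing suggests such a difference: contact with staff is matched between arms (Section 7.1) and the stated reason for moving a test is availability.

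**The case for a change.** The strongest opposing case is that the trial's own controls concede the principle. It supplies a standardised dinner and restricts testing to a menstrual window, yet lets the primary measurement fall outside the dinner control. Matching wherever possible would cost a few sentences and two recorded items, and could add up to about 3.4 points of power (83.58 − 80.15).

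The textual part stands: the note does not exclude FMD, no dinner is stated before Day 1, and nothing matches day or dinner across time points. The claimed gain does not stand. It comes entirely from the value chosen for s; at s = 0 it vanishes, and at s = 0.25 it is 0.10 to 0.21 points. The documents give no purpose for the dinner, and Day 2 also includes a fasting blood draw, so treating the dinner as an FMD control is an inference.

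Nor is matching free. It narrows booking, which the 7-day window already restricts for pre-menopausal women, and a dinner before Day 1 may need a separate pickup. Applied strictly, it could cancel its own gain by losing as few as 0.17 week-12 tests per group at s = 0.25, or 5.56 at the top of the range. Applied softly, it guarantees little.

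**Conclusion.** No change to the plan is needed. The choice between two dinners, and the day a vascular test is booked, are operational details that study staff settle when scheduling; flexible booking is a fair trade for complete week-12 FMD data. Followed as written, the plan still gives a sound primary comparison at its stated power of 80.1%.

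The effect on precision is unknown and may be zero. On the assumed range (25% or 50% mismatched, added SD up to 1.0 point), power would lie between 76.8% and 80.1% if the noise comes on top of SD 2.4. If the nut trials behind the sample size already contained such noise, nothing is lost against plan. The absence of bias assumes that availability on the test days does not depend on arm, which the documents give no reason to doubt.

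Timing points the same way. The SAP, dated September 2023, reports analyses in the past tense, so a matching rule could no longer alter the FMD tests. A matched-subset analysis would keep only 48 or 32 per group at 25% or 50% mismatched, with 67.9% or 50.4% power at SD 2.4, and would select participants after randomisation.

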7.2.3 Day 2 of Baseline and Endpoint Measures

On day 2 of baseline and endpoint visits, which occur approximately 24 hours after day 1 testing, a fasting blood sample will be collected and flow mediated dilation measures will be taken. Body weight will be taken. Fecal sample collection will be brought to the visit by the subject.

Flow mediated dilation: Study subjects will undergo endothelial health assessment by FMD at baseline (beginning of study) and end of each intervention period. The technique of FMD is a non-invasive test that assesses endothelium-dependent dilatation in response to increased blood flow. Blood flow is induced by inflation and deflation of a cuff on the forearm. The cuff should be inflated to suprasystolic pressures in order to occlude the brachial artery. A pressure of 250 mmHg is a standard pressure used by many research groups. B-mode ultrasound is used to assess endothelium-dependent vasodilation.

Plasma/serum analysis: A 12 hour fasting blood sample will be taken. Approximately 45 ml (about 3 Tbsp) will be collected at each visit. A typical American Red Cross blood donation is 1 pint (500 ml). Blood may be analyzed for the following: blood lipids and lipoprotein concentration, particle number and size, glucose and insulin, other markers of glycemia, cholesterol metabolism, and/or inflammation.

7.2.4 Monthly study food or gift card

Monthly, participants will coordinate pick up times for study food or gift card with study personnel at Penn State Metabolic Diet Study Center. Depending on Group, the script on “Usual Care Group Instructions-[name]-6-18-21” or “Pecan Group Instructions-[name]-6-18-21” will be used. Participants will also return compliance tracking sheets at months 2 and 3 (see attached “Daily monitoring form pecan condition-6-18-2021” or “Daily monitoring for usual care condition-6-18-2021) to identify if/when and how the pecans are being consumed.

Daily monitoring form: Participants will complete daily monitoring forms regarding consumption of pecans (test food)/ food consumed during the usual care condition, changes in medication or health during the study. When they pick up their test food monthly, they will be provided with the daily monitoring forms and asked to return the completed forms the next time they pick up food. Participants will also receive a phone call biweekly to ensure compliance.

7.2.5 24-hour dietary recalls

Dietary intake: Three, 24-hour recalls will be administered in the week prior to baseline, week 6, and week 12 of the study using the Automated Self-Administered 24-Hour (ASA24®) Dietary Assessment Tool. This is an online system where participants will provide information about all foods, beverages and supplements consumed during the previous day. This system generates food group and nutrient data from the 24- hour recalls. These data will be used for calculation of diet quality assessed by the Healthy Eating Index 2015 (4).

7.3

Duration of Participation

Describe how long subjects will be involved in this research study. Include the number of sessions and the duration of each session - consider the total number of minutes, hours, days, months, years, etc.

Each participant will be involved in the study for approximately 12 weeks. Pre-menopausal women will be scheduled for testing within 7 days of starting their menstrual period to control for hormonal effects on vascular function; the treatment period will be adjusted accordingly in pre-menopausal women. Participants will be expected to pick up the pecans/gift card monthly at the diet center on campus. Participants will remain in their vehicle and a staff member from the Metabolic Diet Center will bring pecans/gift cards. Compliance monitoring will also be conducted at this appointment. At the beginning and end of the diet period, data collection (described above) will occur.

Total time for study visits, after the initial screening is approximately 3 hours. Times may vary and females will require an additional 5 minutes for a urine pregnancy test a baseline and the end of the diet period. The following is an estimate of the amount of time participants will spend in study activities:

Screening appointment:

Day 1: Forms, blood pressure, weight, height, waist circumference, blood draw – 45-60 minutes
(pregnancy testing: females only – 5 minutes)

Beginning of treatment period:

Day 1: blood draw, weight, waist circumference, vascular testing – 60 minutes
(pregnancy testing: females only – 5 minutes)

Day 2: blood draw, vascular testing – 45 minutes

End of treatment period (week 12):

Day 1: blood draw, weight, waist circumference, vascular testing – 60 minutes
(pregnancy testing: females only – 5 minutes)

Day 2: blood draw, vascular testing – 45 minutes

Picking up food/gift card, fecal collections, and completing 24-hour diet recalls: ~ 7 hours

Total time for clinic and diet center visits from the beginning to the end of the study ~12 hours

8.0 Number of Subjects and Statistical Plan

8.1 Number of Subjects

Indicate the maximum number of subjects to be accrued/enrolled. Distinguish between the number of subjects who are expected to be enrolled and screened, and the number of subjects needed to complete the research procedures if applicable (i.e., numbers of subjects excluding screen failures.)

A sample size of 128 (64 per group) is needed. To complete 128 individuals, approximately 140 participants will be recruited to account for an anticipated ~10% dropout rate.

8.2 Sample size determination

If applicable, provide a justification of the sample size outlined in section 8.1 to include reflections on, or calculations of, the power of the study.

Power analysis for the primary endpoint, FMD, is based on the differences reported in clinical trials of tree nuts (5-8). To detect a 1.2% (standard deviation 2.4; effect size 0.5) between-condition mean difference with 80% power ($\alpha=0.05$), 128 or 64 people per group are needed.

8.3 Statistical methods

Describe the statistical methods (or non-statistical methods of analysis) that will be employed.

The normality of the data will be tested before performing analyses, and transformations will be made if needed. In the primary analyses, the change in outcome measures (baseline to 12 weeks) will be compared between groups after adjustment for baseline value, age, sex, and BMI. The mixed model

procedure will be used (SAS) with randomization as a fixed factor, and baseline value for the outcome measure, age, sex, and BMI included as covariates.

9.0 Data and Safety Monitoring Plan

This section is required when research involves more than Minimal Risk to subjects as defined in “HRP-001 SOP- Definitions.”

Minimal Risk is defined as the probability and magnitude of harm or discomfort anticipated in the research that are not greater in and of themselves than those ordinarily encountered in daily life or during the performance of routine physical or psychological examinations or tests. For research involving prisoners, Minimal Risk is the probability and magnitude of physical or psychological harm that is normally encountered in the daily lives, or in the routine medical, dental, or psychological examination of healthy persons.

Please complete the sections below if the research involves more than minimal risk to subjects, otherwise indicate each section as not applicable.

[Do not type here]

9.1 Periodic evaluation of data

Describe the plan to periodically evaluate the data collected regarding both harms and benefits to determine whether subjects remain safe.

Not applicable

